TITLE:

The effect of probiotics in non-alcoholic fatty liver disease and steatohepatitis measured by transient elastography

NCT 04175392

Approval date: 04/07/2021

Study Protocol and Statistical Analysis Plan

Title: Effect of probiotics in non-alcoholic fatty liver disease and steatohepatitis measured by transient elastography (PRONE Study)

FDA IND Exempt

Principal Investigator: [name], DO

Co-Investigators: [name], DO and [name], DO

Institutional Affiliations: Beaumont Health, Farmington Hills

BACKGROUND AND SIGNIFICANCE

Non-alcoholic fatty liver disease (NAFLD) and Non-alcoholic steatohepatitis (NASH) are usually conditions without symptoms where inflammation in the liver can progress to end-stage liver disease (Cirrhosis). Current standard of care for these conditions include control of metabolic syndrome which includes but is not limited to a patient's high blood pressure (hypertension), high cholesterol (hyperlipidemia), high blood sugar (hyperglycemia) and excess fat around the waist (central obesity and waist circumference) with lifestyle modifications including diet, exercise and medications.

Previous trials have identified equivocal results with Vitamin E and Pioglitazone (an oral diabetic drug). Some patients do not see results and we still see increased liver enzymes known as transaminases. Other studies suggest that there is a role for the Mediterranean diet in managing NAFLD, but further research is indicated. While the mechanism for inflammation on the liver in NAFLD and NASH is not completely understood, the American Association for the Study of Liver Diseases currently suspects it may be connected with the metabolism in the bowel and subsequent hepatic (liver) circulation.

The bacteria of the intestines (microbiome or gut flora) may play a role in the inflammatory cascade through the bloodstream that affects the liver [1]. Related studies on hepatic function following administration of probiotics by Wong et al. (2013) and Aller (2011) over 6 and 3 months duration demonstrated statistically significant changes.

OBJECTIVES

Our hypothesis is that introducing a benign probiotic (beneficial intestinal bacteria) using Align probiotics will cause improvement in hepatocellular (liver tissue) injury and fibrosis. Align is a once daily over-the-counter defined by the Food and Drug Administration as a new dietary ingredient. Each Align capsule contains one billion beneficial live bacteria/CFU, known as Bifidobacterium 35624. Our goal is to provide data that probiotics may be a viable treatment option in the future for clinicians for NAFLD and NASH and to establish a link that the intestinal microbiome plays a role in liver inflammation.

IRB NUMBER: 2019-129
IRB APPROVAL DATE: 04/07/2021

Primary Endpoint:

To determine if probiotic use improves fibrosis stage on transient elastography

Secondary Endpoints:

To determine if probiotic use improves:

- 1) Liver Enzymes (AST and ALT)
- 2) Hemoglobin A1C (Diabetic Marker)
- 3) BMI (Body Mass Index)
- 4) Lipids (LDL)

METHODS

NAFLD and NASH patients seen in office consultation at South Oakland Gastroenterology Associates in Farmington Hills, Michigan from 2019-2021 who have confirmed diagnosis of NAFLD or NASH and fit the eligibility requirements will be approached to participate in the double-blind, placebocontrolled study.

After preparation and randomization by the Beaumont research pharmacy, the probiotic and placebo capsules will be delivered to the office in groups of 10 bottles at a time. Capsule bottles will be numbered consecutively and pharmacy will keep the randomization log; patients and researchers will be blinded. The bottles will be stored in a locked cabinet in the clinic. Only pharmacy will hold the randomization key. A log will be used to track the receipt and distribution of the capsules.

After informed consent is obtained, subjects will be counseled on diet and exercise and a baseline transient elastography exam will be ordered and baseline liver enzymes (AST and ALT) will be drawn, including hemoglobin A1C, lipids in the form of LDL and assessment of BMI (all standard of care tests). The patients will receive information on a standardized Mediterranean diet based nutrition program as well as direction for recommended 30 minutes of aerobic exercise 3 times weekly. Our recommended nutrition program limits excessive alcohol to avoid a confounding variable.

Patients will be randomized by pharmacy into 2 groups, a control group and a treatment group. The treatment group will be provided with a 6 month supply of probiotic supplementation; the control group will be given a placebo for 6 months along with instructions on how to take the supplement. Subjects will receive a 1 month (+/- 1 week) phone call follow up to ensure adherence to study instructions and daily oral intake of supplement and again at 3 months (+/- 1 week).

Study participation will end at 6 months (+/- 2 weeks) after the repeat of liver enzymes, hemoglobin A1C, lipid panel, assessment of BMI and transient elastography as completed at scheduled clinical appointment.

TABLE OF EVENTS

	Pretreatment	1 month +/-1 week	3 month +/-1 week	6 month +/-2 weeks
Consent	Х			
Capsules dispensed	Х			
Diet & exercise plan explained	Х	Х	Х	
Labs drawn	Х			Х
Liver scan done	Х			Х
Phone call		Х	Х	
Remaining capsules returned				Х

RISKS AND BENEFITS

The FDA has identified the study as minimal risk and exempt of the need for an IND number.

There are currently no alternative treatments or procedures indicated in this disease process, hence, the purpose of the study. However, potential benefits to subjects from exercise (walking) intervention and nutritional coaching may improve the elasticity and function of the liver.

Potential risks include GI symptoms related to probiotic use such as gas and bloating. The recommended exercise is walking.

VI. ELIGIBILITY CRITERIA

Inclusion Criteria:

- Diagnosis of NAFLD and/or NASH
- Subject aged 18 and older
- Non-pregnant Self-reported
- Subject with decision making capacity to understand and consent to study procedures
- Ability to follow study related activities regarding medications, diet and exercise

Exclusion Criteria:

• Without diagnosis of NAFLD or NASH

- History of liver disease from other causes, including but not limited to hepatitis, autoimmune, alcohol use, fatty liver of pregnancy, Wilson's disease, primary or secondary hemochromatosis
- Patients aged less than 18 years
- Self-reported pregnant patients
- Inability to understand, follow and consent to study procedures
- Received a liver scan greater than 2 months prior to enrollment
- Patient lost more than 5 pounds of weight in the last 2 months
- Hepatic decompensation defined as gastrointestinal bleeding, ascites, hepatic encephalopathy
- Inability to engage in exercise
- Currently immunocompromised or taking immunosuppressive drugs
- Milk protein allergy
- Recent or active chemotherapy for malignancy
- Gastrointestinal malignancy
- Gastrointestinal disease such as Ulcerative Colitis, Crohn's Disease as these alter the microbiome
- Recent antibiotic therapy (within 6 months)
- Known allergy to probiotics
- History of major gastrointestinal surgery such as resection of the colon
- No concomitant use of probiotic from any source (i.e., kefir, certain yogurts, live culture sauerkraut)
- Any implanted battery operated device (i.e. AICD, pacemaker, loop recorder, cochlear implant)

DATA COLLECTION

Any changes to the liver will be documented using a non-invasive scan called transient elastography. Elastography is a technique similar to ultrasound that measures the stiffness and density of the liver and is a safer alternative to a liver biopsy. This is a standard of care procedure will be done at 0 months and 6 months. Along with the scans, the results of liver enzymes, standard of care laboratory tests used to follow the disease progression for patients with NAFLD and NASH, will be reviewed. These labs include AST and ALT, Hemoglobin A1C, BMI (Body Mass Index) and Lipids (LDL), also standard of care.

DATA ANALYSIS

A. Sample Size Consideration

Using paired measurements, a two-tail alpha of 0.05, a power level of 0.8, and assuming a large effect size (contingency coefficient of 0.447), it is estimated that 40 subjects (20 per group) would detect statistically significant between-group changes in liver function. Related studies on hepatic function (Wong, et al., 2013 and Aller, et al. 2011) following administration of probiotics over 6 and 3 months 03.30.2021

IRB APPROVAL DATE: 04/07/2021

duration demonstrated statistically significant changes with estimated large effect sizes using 20 and 28 subjects, respectively. A sample size of approximately 40 is expected to hold statistical significance, however, to account for dropouts or potential removal of subjects from study, a goal of 80 subjects are expected to be enrolled to ensure adequate sample size.

B. Statistical Methodology

Categorical data will be summarized as counts and percentages, and continuous data as means with corresponding standard deviations. Pre- post- results will use the chi-square test for association for nonparametric data or analysis of covariance for parametric data. Because multiple measures will be obtained for achieving the secondary objectives, multivariate analyses will be used for exploring overall treatment effects. Throughout this study, a p-value<0.05 (two-tail) will be considered statistically significant.

DATA AND SAFETY MONITORING PLAN

The Principal Investigator and the co-investigators will do safety monitoring. Ongoing assessment of subject safety will be monitored during subject phone calls as detailed in methodology. Any reported problems will be discussed with Medical Monitor/ Principle Investigator. Subjects with any signs or symptoms of hepatic decompensation or elevated liver enzymes beyond three times the upper limit of normal will be removed from the study, the study will be aborted for that subject and immediate diagnostic and/or therapeutic modalities will be delivered. It should be noted that our study is defined as minimal risk as also identified by the FDA with the exemption of need for an IND number.

Any subject found to be noncompliant with the protocol will be removed from the study and asked to return their medications to the office. The medications will then be returned to the research pharmacist.

All data will be kept electronically in a secure SharePoint site. Hard copies will be kept in a locked file located in a locked office until the study ends. Hard copies will then be scanned into the SharePoint site and shredded per Beaumont policy.

REFERENCES

[1] The Liver Meeting, Post-Graduate Seminar, New Research, American Association for the Study of Liver Diseases, Washington, D.C., 2017

Velasco, Nicolas; Contreras, Alvaro; Grassi, Bruno. The Mediterranean diet, hepatic steatosis and nonalcoholic fatty liver disease. Current Opinion in Clinical Nutrition & Metabolic Care. 17(5):453-457, September 2014.

Attachments

- A. PRONE Study Informed Consent Form and Authorization for Disclosure of Protected Health Information
- B. PRONE Study FDA 2018-1186 Signed Final Response
- C. PRONE Study Nutrition Program
- D. PRONE Study Exercise suggestions
- E. PRONE Study Pharmacy Budget Estimate

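### Fibrosis stage, the primary endpoint, has no test assigned to it; the plan's rule and sizing point to an unadjusted chi-square, and an ordered, baseline-adjusted analysis would use the two scans better

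*Combined protocol and SAP*

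**What the plan says.** - **Endpoint.** Under Objectives, the single primary endpoint is "To determine if probiotic use improves fibrosis stage on transient elastography". The secondary endpoints are liver enzymes, haemoglobin A1C, BMI and LDL, so stage is the only endpoint taken from the scan. Stage cut-points and the scoring of improvement are not given.
- **Scan.** Data Collection states: "Elastography is a technique similar to ultrasound that measures the stiffness and density of the liver". Scans are planned at 0 and 6 months. Stiffness is not listed as an endpoint.
- **Entry.** The eligibility section asks for "Diagnosis of NAFLD and/or NASH" and sets no minimum fibrosis stage.
- **Test.** Data Analysis, B. Statistical Methodology says that pre/post results "will use the chi-square test for association for nonparametric data or analysis of covariance for parametric data". It does not say which of the two applies to fibrosis stage.
- **Sizing.** Data Analysis, A. Sample Size Consideration works at two-sided 0.05 and 80% power, "assuming a large effect size (contingency coefficient of 0.447), it is estimated that 40 subjects (20 per group"). The enrolment goal is 80, to allow for losses. The same sentence refers to paired measurements and to liver function, not to fibrosis stage.

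**The concern.** Stage is a categorical outcome. Under the plan's rule it would most naturally fall to the chi-square, and the contingency coefficient is a chi-square effect size. A chi-square treats the categories as unordered. If it is run on improved/same/worse or on improved yes/no, baseline enters the scoring but is not adjusted for. A subject who starts in the lowest stage cannot improve by stage, and with no minimum stage at entry such subjects may be numerous.

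With 20 per arm there is little information to spare. If the chi-square is used, a null result on the primary endpoint could reflect the test and not the lack of an effect. If the choice of test stays open, it could be made after the results are seen.

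**Working it through.** **1. The plan's own figure.** Inputs from the Sample Size Consideration: C = 0.447, alpha 0.05 two-sided, power 0.80, N = 40.

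w = C/√(1 − C²) = 0.447/√(1 − 0.1998) = 0.4997. Power comes from the noncentral chi-square with λ = N·w²; at N = 40, λ = 40 × 0.2497 = 9.99.

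| df | N for 80% power | Power at N = 40 |
|---|---|---|
| 1 | 32 | 0.885 |
| 2 | 39 | 0.815 |
| 3 | 44 | 0.761 |
| 4 | 48 | 0.715 |

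So 40 is reproduced with 2 df (39, rounded up to equal arms), which would be two groups by three categories. It is also reproduced if 0.447 is entered directly as w with 1 df: N = 39.3, rounded up to 40, power 0.807. Both are chi-square sizings, but the table cannot be identified.

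**2. Comparing the analyses on the same data.** The documents give no SD, correlation or stage mix, so every input here is assumed.
- Baseline and 6-month stiffness are standard normal with correlation 0.7.
- Stiffness is cut into five stages, with 30/50/70% of subjects in the lowest and the rest split equally.
- The probiotic shift is (a) the same at every stage, (b) halved in the lowest baseline stage, or (c) absent there.
- There are 10,000 trials per cell, tested at two-sided 0.05.
- Adjusted stage is a linear model of the 6-month stage score on arm and baseline stage. Stiffness is ANCOVA on baseline stiffness.

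Power in %, for 30/50/70% in the lowest stage:

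| Shift, per arm, case | Chi-square, improved/same/worse | Adjusted stage | Gain (points) | Stiffness ANCOVA |
|---|---|---|---|---|
| 0.5 SD, 20, (a) | 24.7/19.4/13.2 | 43.8/35.3/24.0 | 19.1/15.9/10.8 | 56.8/56.0/57.1 |
| 0.5 SD, 20, (b) | 20.2/14.9/9.5 | 36.2/27.9/17.5 | 16.0/13.0/8.0 | 42.6/35.4/27.9 |
| 0.5 SD, 20, (c) | 18.2/10.8/6.7 | 30.2/18.5/10.4 | 12.0/7.7/3.7 | 32.1/17.9/9.7 |
| 0.8 SD, 20, (a) | 49.4/38.0/22.2 | 79.3/66.9/45.8 | 29.9/28.9/23.6 | 92.6/92.3/92.6 |
| 0.8 SD, 20, (c) | 34.2/18.6/10.1 | 58.9/36.9/18.2 | 24.7/18.3/8.1 | 63.7/37.0/17.2 |
| 0.5 SD, 40, (a) | 47.0/39.5/28.6 | 73.4/63.3/46.8 | 26.4/23.8/18.2 | 86.5/86.8/86.9 |
| 0.5 SD, 40, (c) | 33.4/19.1/10.7 | 53.1/33.5/17.8 | 19.7/14.4/7.1 | 56.2/32.6/15.0 |

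With no effect, rejection was close to 5% for every method, so the gain is not bought with false positives.

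**3. The other candidate table.** With improved yes/no in the same model, adjusted stage was again ahead in every non-null cell. At 0.5 SD, 20 per arm, case (a), 30% lowest, the figures are 44% for adjusted stage, 22% for yes/no and 23% for three categories in the same run (24.7% in the table above). At 20 per arm the smallest gain over yes/no was 0.107 − 0.081 = 0.026 (0.5 SD, case (c), 70% lowest). The largest was 0.674 − 0.238 = 0.436 (0.8 SD, case (a), 50% lowest). Over both tables, the gain at 20 per arm is therefore about 3 to over 30 points.

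**4. Sensitivity (against the three-category table, 0.5 SD, 20 per arm).** At correlation 0.5, case (c), 70% lowest, the gain falls to 0.078 − 0.065 = 0.013. At correlation 0.8, case (a), 30% lowest, it is 0.527 − 0.318 = 0.209. With three stages at correlation 0.7 it runs from 0.102 − 0.072 = 0.030 in case (c), 70% lowest, to 0.381 − 0.212 = 0.169 in case (a), 30% lowest.

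**5. What stiffness adds to adjusted stage.** In case (a), 0.5 SD, 20 per arm, it adds 56.8 − 43.8 = 13 points at 30% lowest and 57.1 − 24.0 = 33 at 70%. In case (c) with five stages at correlation 0.7, the difference lies between −3 points (15.0 − 17.8) and +5 points (63.7 − 58.9). With three stages, case (c), 30% lowest, it is about 8 points at 20 per arm (0.316 − 0.241) and 13 at 40 (0.565 − 0.436).

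**The case against.** **The comparator is inferred.** The documents never mention an improved/same/worse table, and N = 40 fits a yes/no table as well. This stands as a limit on the exact percentages. It does not change the direction, because adjusted stage beat both tables.

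**ANCOVA is already in the plan.** This is true, and it means the plan does not lack a baseline-adjusted method; it fails to link one to the primary endpoint. A reader might infer that the chi-square is the settled primary test. The documents do not say so: the evidence is a general rule and a sizing sentence that itself speaks of paired measurements and liver function.

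**Every power input is assumed, and the model favours stiffness.** It makes stiffness exactly normal and stage a plain cut of it, with no skew or outlying readings. This also stands. The figures are an illustration, and where most subjects are in the lowest stage and do not respond, no analysis has useful power.

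**Stiffness should be primary.** A reader might infer this from the case (a) figures. The documents do not support it. The stated question is improvement in stage, and mean stiffness is a different question. Where the lowest stage does not respond, stiffness gains little over adjusted stage, and nothing in the documents says whether that stage responds. Another test at 0.05 would also raise multiplicity unless its role is fixed as supportive.

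**Conclusion.** The point holds in a limited form. No test is assigned to the primary endpoint, the plan's rule and sizing point to an unadjusted chi-square, and that test makes poor use of an ordered outcome with a baseline already measured. An ordered, baseline-adjusted analysis of stage had more power in every case run. At correlation 0.7 with five stages and 20 per arm, the gain ran from about 3 to over 30 points; at correlation 0.5 it could shrink to about 1 point. These sizes rest wholly on the assumed shift, correlation, number of stages, stage mix and response in the lowest stage. The direction is better supported than the size.

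It would be wrong to read this as saying that 40 was miscalculated. It reproduces as a chi-square sizing; what is missing is the table it refers to. This is a change the sponsor should make, with medium confidence. If ANCOVA was always meant for stage, the gap against the chi-square disappears and only the stiffness analysis is new.

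**What to change.** Before unblinding:

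1. Keep fibrosis stage as the primary endpoint and state its cut-points.
2. Name one primary analysis: 6-month stage as an ordered outcome, compared between arms with adjustment for baseline stage, in place of an unadjusted chi-square. Name the model; the power figures above are for a linear model of the stage score. If ANCOVA on stage was already intended, say so.
3. Add 6-month liver stiffness, by ANCOVA with baseline stiffness as covariate on a scale fixed in advance (for example log), as a named supportive secondary analysis. State that it cannot replace the primary result, so that no extra multiplicity arises for the primary claim.
4. In the sample-size paragraph, state the table and degrees of freedom behind the 40.

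**Cost.** An IRB-approved amendment, possibly during the trial: Methods describes patients seen "from 2019-2021 who have confirmed diagnosis of NAFLD or NASH", and this version carries "IRB APPROVAL DATE: 04/07/2021". It can be made blind, since "Only pharmacy will hold the randomization key". No new procedure is needed, but the stiffness value must be recorded at both scans.

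### No entry rule or record covers changes in glucose-lowering drugs, lipid-lowering drugs, vitamin E or pioglitazone, which costs precision on the secondary endpoints

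*Combined protocol and SAP*

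**What the plan says.** Background and Significance describes standard care as control of the metabolic syndrome, including cholesterol and blood sugar, "with lifestyle modifications including diet, exercise and medications". It adds: "Previous trials have identified equivocal results with Vitamin E and Pioglitazone (an oral diabetic drug". No other agent or class is named there. Risks and Benefits says: "There are currently no alternative treatments or procedures indicated in this disease process".

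Section VI (Eligibility Criteria) excludes "Patient lost more than 5 pounds of weight in the last 2 months", antibiotics within 6 months, other probiotics, immunosuppressive drugs and recent chemotherapy. It has no criterion on stable use of lipid-lowering or glucose-lowering drugs, vitamin E or pioglitazone. The one inclusion criterion that mentions medications concerns ability to follow study activities and is not a stable-dose rule.

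The Table of Events and Data Collection list scans, laboratory tests, BMI, capsules and calls, but no medication record. The calls at 1 and 3 months cover adherence, diet and exercise, and safety. Statistical Methodology offers a chi-square test or an analysis of covariance without naming covariates, and no stratification is stated.

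The secondary endpoints are AST/ALT, HbA1c, BMI and LDL. The primary endpoint is fibrosis stage on elastography.

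**The concern.** The protocol already accepts that recent influences on the endpoints should be screened out: it does so for weight loss, antibiotics and other probiotics, and its nutrition program limits alcohol so as to avoid confounding. Drugs given for cholesterol and blood sugar act directly on LDL and HbA1c, but they are left out. A patient who began one shortly before consent is eligible, and baseline adjustment does not remove a drug effect that develops after the baseline draw.

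Two things are at stake. The secondary comparisons become noisier in a trial sized at 20 evaluable subjects per group. In addition, the planned data would not show who changed a drug, so neither the balance between arms nor the robustness of the result could be examined from them.

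**Working it through.** **1. The plan's own figure.** Sample Size Consideration uses "a two-tail alpha of 0.05, a power level of 0.8" and "assuming a large effect size (contingency coefficient of 0.447", and concludes: "it is estimated that 40 subjects (20 per group) would detect statistically significant between-group changes in liver function". Taking 0.447 directly as the chi-square effect size w with 1 degree of freedom, the noncentrality at N = 40 is 40 × 0.447² = 7.99 and power is 0.807, so 40 reproduces. Converting the contingency coefficient, w = 0.447/√(1 − 0.447²) = 0.4997, gives N = 39 with 2 degrees of freedom. The plan does not say which reading it used. Neither reading allows for drug changes.

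**2. Assumed inputs.** The documents give no rate of drug change and no effect on any marker. Let p be the share of subjects with a recent or on-study change, and d the resulting shift in SDs of the marker's 6-month change. Assumed range: p = 10% to 20%, d = 1 to 2. Milder case: p = 10%, d = 0.5.

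**3. Variance.** With the same p in both arms, the variance factor is V = 1 + p(1 − p)d².

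**4. Power.** By the two-sample noncentral t, 20 per arm gives 80% power for a difference of 0.91 SD. With drug changes the standardised difference becomes 0.91/√V.

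| p | d | V | 40/V (effective N) | 0.91/√V | Power, 20 per arm |
|---|---|---|---|---|---|
| none | – | 1 | 40 | 0.910 | 0.80 |
| 10% | 0.5 | 1 + 0.09 × 0.25 = 1.02 | 39.1 | 0.900 | 0.79 |
| 10% | 1 | 1 + 0.09 × 1 = 1.09 | 36.7 | 0.872 | 0.77 |
| 20% | 1 | 1 + 0.16 × 1 = 1.16 | 34.5 | 0.845 | 0.74 |
| 20% | 2 | 1 + 0.16 × 4 = 1.64 | 24.4 | 0.711 | 0.59 |

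**5. Chance imbalance.** Take p = 15%. For two independent Binomial(20, 0.15) counts, the probability of a gap of 3 or more subjects (15 percentage points) is 0.26. At 40 per arm the same 15-point gap is 6 subjects, with probability 0.08.

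**6. What such a gap does.** A 3-in-20 gap moves the difference between arms by 0.15 × d, that is 0.15 SD (d = 1) to 0.30 SD (d = 2). The standard error without inflation is √(2/20) = 0.316 SD, so the shift is 0.47 to 0.95 standard errors.

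**7. Bias.** Simulated trials with 20 per arm, no treatment effect and equal change rates in both arms gave a mean difference of about 0 and type I error of 0.049 (p = 20%, d = 1, and likewise p = 30%, d = 1.5). The nominal error rate is kept.

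**The case against.** The strongest reply is that a randomised, double-blind comparison already handles background drugs: chance imbalance is part of what the 5% error rate covers. That stands. A reader might infer that drug changes confound the probiotic effect, or that a few of them could by themselves create a significant result. The documents do not support either. Steps 6 and 7 show no bias on average and a typical gap worth less than one standard error.

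A reader might also take the protocol to name particular drugs as care for this disease. It does not: medications appear generically under standard care, and vitamin E and pioglitazone are cited for equivocal results. Nor do the criteria require stable weight, since only loss of more than 5 pounds excludes.

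The sizes rest on assumed inputs, and 20 per arm is the plan's minimum: "a goal of 80 subjects are expected to be enrolled to ensure adequate sample size". If all 80 were evaluable, the 15-point gap would be rarer (8% against 26%) and absolute power higher. That is fair, but the plan's power statement rests on 40.

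It is also not shown that drug histories would be irretrievable, because subjects are patients of one practice under routine care. What stands is narrower: the plan collects no such data prospectively.

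Finally, removing subjects from an analysis because of an on-study drug change conditions on a post-randomisation event and can introduce selection. That is correct, and it limits the role of any such analysis.

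**Conclusion.** The gap is real, and nothing else in the documents fills it: there is no stability rule, medication record, stratification or drug covariate. Its consequence is lost precision and chance imbalance on LDL, HbA1c, BMI and AST/ALT, not systematic bias. Under the assumed 10% to 20% of subjects shifting by 1 to 2 SD, the variance of an affected marker rises 9% to 64%, and power for a 0.91 SD difference at 20 per arm falls from 80% to about 77% to 59%. Under the milder assumption the loss is about 1 percentage point. The documents cannot say where in this range the trial lies. For the primary endpoint an effect is possible, but no figure can be given.

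The Background statement that standard care includes medications and the Risks and Benefits statement that no alternative treatments are indicated do not sit together and must be reconciled. This review does not say which is right. Overall this is a cheap improvement that should be made, not a flaw that invalidates the comparison.

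**What to change.** - **Entry.** Beside the weight criterion, add an exclusion for a start, stop or dose change of a glucose-lowering drug, lipid-lowering drug, vitamin E or pioglitazone within the 2 months before enrolment, which is the window already used for weight loss.
- **Recording.** Record these drugs at pretreatment, at the 1- and 3-month calls and at month 6, and add the line to the Table of Events. The entry rule covers only changes before enrolment; on-study changes are recorded, not prevented, and routine care is not restricted. The rule alone therefore recovers only part of the loss shown above.
- **Analysis.** Keep all randomised subjects in the main analysis and report drug changes by arm. Treat any analysis that excludes or adjusts for on-study changes as supportive only, and state that it conditions on a post-randomisation event.
- **Text.** Reconcile the Background and the Risks and Benefits statements on available treatment.

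The cost is one criterion and one line on existing forms. The downside is that patients in active titration wait about 2 months, which slows enrolment slightly; the documents do not allow an estimate of how many would be affected.

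### Over-enrolment is the plan's only provision for lost subjects; it protects the count, but not the comparability of the arms in what is by implication a completers-only primary comparison

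*Combined protocol and SAP*

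**What the plan says.** The primary endpoint under OBJECTIVES is "To determine if probiotic use improves fibrosis stage on transient elastography". METHODS places the single repeat assessment at the end of follow-up: "Study participation will end at 6 months (+/- 2 weeks) after the repeat of liver enzymes, hemoglobin A1C, lipid panel, assessment of BMI and transient elastography". The TABLE OF EVENTS and DATA COLLECTION agree that the liver scan is done twice, at baseline and at month 6, with nothing between. The contacts at months 1 and 3 are phone calls.

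DATA ANALYSIS, section A, works with "a two-tail alpha of 0.05, a power level of 0.8", "assuming a large effect size (contingency coefficient of 0.447", and concludes that "it is estimated that 40 subjects (20 per group) would detect statistically significant between-group changes in liver function". It then sets the enrolment target: "to account for dropouts or potential removal of subjects from study, a goal of 80 subjects are expected to be enrolled to ensure adequate sample".

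DATA ANALYSIS, section B, gives the test: "Pre- post- results will use the chi-square test for association for nonparametric data or analysis of covariance for parametric data". It names no analysis population, no rule for a missing month-6 stage and no sensitivity analysis. The DATA AND SAFETY MONITORING PLAN adds that noncompliant subjects and those meeting safety criteria are removed from the study. It does not say whether they are still scanned at month 6.

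**The concern.** A subject who drops out or misses the month-6 scan has no post-baseline fibrosis stage, and no interim scan can stand in for it. A pre-post chi-square or analysis of covariance without imputation can use only subjects with both scans. The plan does not state this exclusion; it follows from the schedule and the named tests.

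Replacing lost subjects restores the number analysed. It does not restore the balance that randomisation gave if those who stay differ between the arms in ways that bear on the outcome. RISKS AND BENEFITS gives two reasons to keep this possibility open. The capsule-related risks it names are gas and bloating with the probiotic, which could make dropout differ by arm. It also says that the exercise and nutrition components may themselves improve the liver, so that staying in the study and improving could share a cause. At stake is whether a difference among completers can be read as an effect of the probiotic.

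**Working it through.** **1. The plan's own figures.** Inputs from DATA ANALYSIS, section A: two-sided alpha 0.05, power 0.80, contingency coefficient C = 0.447, 40 evaluable, 80 enrolled.

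- Effect size: w = C/sqrt(1 - C²) = 0.447/sqrt(1 - 0.1998) = 0.4997.
- Noncentral chi-square, N = lambda/w²: 2 degrees of freedom give 39 (power at 40 is 0.815), and 1 degree of freedom gives 32 (power at 40 is 0.885). Using 0.447 directly as w with 1 degree of freedom gives 40. The plan does not state the degrees of freedom, but 40 is reproducible under standard variants.
- Reserve: 40/(1 - 0.50) = 80, so the implied combined loss is 50%. For comparison, 40/(1 - d) gives 45 at 10% loss, 50 at 20%, 58 at 30% and 67 at 40%.

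The count is therefore well protected. What remains is comparability.

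**2. What missing stages leave open without further assumptions.** Treat the outcome as stage improved or not (an assumption, as the plan does not define it so). If a share m of each arm is missing and the completers' rate is r, the arm's full rate lies between (1 - m)r and (1 - m)r + m, a width of m. The between-arm difference is then undetermined over a width of 2m: 20 points at 10% missing, 50 points at 25%, and 100 points at 50%.

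**3. Illustration of bias under no probiotic effect.** All rates here are assumed; none is in the documents. There are 40 randomised per arm. Half of each arm follows the lifestyle plan and improves with probability 45%; the rest improve with probability 15%, so the true rate is 30% in both arms. With retention a among followers and b among non-followers, the expected completers' rate is (0.45a + 0.15b)/(a + b).

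| Retention on probiotic (followers/non-followers) | Retention on placebo | Completers improved | Bias (points) | Rejection at nominal 5% |
|---|---|---|---|---|
| 50%/50% | 50%/50% | 30% v 30% | 0 | about 5% |
| 80%/20% | 80%/20% | 39% v 39% | 0 | about 5% |
| 90%/70% | 80%/80% | 31.9% v 30% | +1.9 | about 5.4% |
| 60%/40% | 50%/50% | 33% v 30% | +3 | about 5.6% |
| 80%/20% | 50%/50% | 39% v 30% | +9 | 9% to 10% |
| 75%/5% | 60%/60% | 43.1% v 30% | +13.1 | about 14% |

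Example, fifth row: (0.45 × 0.80 + 0.15 × 0.20)/(0.80 + 0.20) = 0.36 + 0.03 = 0.39. Rejection rates are simulated, using an uncorrected 2×2 chi-square on completers. Expected scans per arm are 40(a + b)/2. That is 20 in every row except the third (32 per arm) and the last (16 on probiotic, 24 on placebo).

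**4. Would imputation from baseline values remove it?** Not in this model. Following the lifestyle plan arises after baseline and is not among the baseline measurements. Within-arm imputation therefore returns the completers' rates: in the fifth row, 0.5 × 39% + 0.5 × 39% = 39% against 30%, still +9 points.

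**The case against.** The strongest reply is that nothing shows dropout will be either large or selective. Several parts of it stand.

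- A reader might infer that half the subjects are expected to drop out voluntarily. The documents do not support that. The reserve covers removals as well as dropouts, no rate is stated, and 80 may simply be a generous target.
- A reader might take a 10% or 14% false-positive rate as the likely consequence. Those figures need strong lifestyle-selective retention on probiotic and none on placebo. Gas and bloating might raise dropout on probiotic, but nothing suggests that they drive out mainly those not following the diet and exercise plan. METHODS blinds patients and researchers, which limits differential dropout though it does not prevent symptom-driven dropout. The calls at months 1 and 3, and a month-6 assessment tied to a scheduled clinical appointment, also help retention.
- Counting missing subjects as not improved does not demonstrate bias. Taking 13/20 v 6/20 (65% v 30%, chi-square 4.91, p = 0.027) to 13/40 v 6/40 (32.5% v 15%, chi-square 3.38, p = 0.066) halves the difference from 35 to 17.5 points even if dropout is purely random. That is dilution.
- Nor is every such subject lost to all secondary measures. Labs and scan are separate rows in the TABLE OF EVENTS, so someone who misses only the scan may still have the rest.

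What does not stand is that extra enrolment deals with the problem. It addresses precision only, and no other provision appears in the documents.

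**Conclusion.** The point holds in a limited form. Over-enrolment is the plan's only answer to lost subjects, and the primary comparison is by implication restricted to those with both scans. Power is protected (0.815 at 40 under 2 degrees of freedom); comparability is not, if dropout is related to arm and outcome.

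The size of any bias cannot be known from the documents. In the illustration it runs from zero (retention unrelated to outcome, or the same lifestyle pattern in both arms), through about +3 points (mild one-arm selection), to +9 to +13 points (strong one-arm selection only). It shrinks as fewer subjects are lost. The result rests on assumed improvement and retention rates and on a binary reading of the endpoint. The stronger conclusion, that a significant result would reflect who stayed and not the probiotic, does not follow; the plan simply gives no means of telling. This should be corrected because the remedy is cheap and, if loss approaches the reserve, the primary result would be hard to interpret without it.

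**What to change.** In DATA ANALYSIS, section B, state that:

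- the primary comparison is by assigned arm;
- every randomised subject who stops capsules or drops out, and who still consents to contact, is asked to attend the already scheduled standard-of-care month-6 scan and labs;
- dropout and its reasons are reported by arm;
- a tipping-point sensitivity analysis varies the improvement rate among subjects with no month-6 stage, separately by arm.

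Multiple imputation from baseline values may be added as a secondary analysis. It should not be presented as curing the bias, because it does not capture adherence after baseline.

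In section A, state that 80 allows for a combined 50% loss from dropout and removal, and that this protects precision only.

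An analysis of all randomised subjects and the removal rules in the DATA AND SAFETY MONITORING PLAN must be reconciled, so that it is clear how removed subjects enter the comparison. This concerns data handling only and asks for no change to the removal criteria.

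The cost is some reminder calls, a little more analysis work, and a result that may look less certain than a completers-only test. No extra subjects or new procedures are needed.
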